4.4.3.17.1 OLE Phase

This analysis will be repeated to include the EDSS assessments performed during the OLE period for the combined DB+OLE period, with the same baseline as for the analysis during DB. Analysis containing only data from OLE will be performed considering the OLE baseline.

4.4.3.18 Proportion of Patients Who have Disability Improvement Sustained for at Least 12 Weeks and Sustained until the End of the 96-Week, Double-Blind, Double-Dummy Treatment Period, with the Initial Event of Neurological Improvement Occurring during the 96-Week, Double-Blind, Double-Dummy Treatment Period

This endpoint is similar to the 12-week confirmed disability improvement endpoint (see Section 4.4.2.6), but it is required that improvement is sustained until the end of the 96-

week double-blind double-dummy treatment period. Otherwise, patients will be classified as not improved.

The same approach to analysis as described in Section 4.4.2.6 will be applied here.

4.4.3.19 Duration of Confirmed Disability Improvement

This analysis will be performed for the patients with a Confirmed Disability Improvement for 12 weeks identified as in Section 4.4.2.6.

The duration of the Confirmed Disability Improvement is the time from the date of onset of the event, until the first visit where the EDSS score no longer fulfills the criteria for disability improvement. For the patients who have a sustained improvement until after the end of the double-blind treatment period, the duration of the confirmed disability improvement will be censored at the last EDSS score measured during the 96 week, double-blind, double-dummy treatment period. For patients with the onset of the CDI at the last visit during this period and confirmed in the open-label or safety follow-up phase, the duration of the CDI will be censored at Day 1. The Kaplan-Meier estimates of the duration of CDI will be calculated. No comparison between the randomized arms will be made, since this analysis is performed only for the patients with a CDI.

4.4.3.20 Proportion of Patients Who at Week 96 Have Improved, Stable or Worsened Disability, Compared with Baseline

Stable disability is defined as a difference in EDSS score of no greater than ± 0.5 comparing the Week 96 and baseline scores. Worsened disability is defined as an increase in EDSS score of > 0.5 at Week 96 compared to baseline. Improved disability is defined as a reduction in EDSS score of > 0.5 at Week 96 compared with baseline. The proportion of patients with improved, stable, or worsened disability compared with baseline in each treatment group will be reported. In addition, the proportion of patients with improved or stable disability (combining the proportion of patients improved and the proportion stable) in each treatment group will be reported.

Patients with missing EDSS data at baseline or Week 96 are excluded from this analysis. Interval EDSS scores are not taken into account in this analysis.

The proportions with improved, stable, and worsened disability within treatment groups will be analyzed using multinomial logistic regression with baseline covariates, geographical region (United States vs. ROW), and baseline EDSS score (< 4.0 vs. ≥ 4.0).

4.4.3.21 Change in EDSS Score from Baseline to Week 96

The EDSS scores will be summarized at baseline (without rounding) and Weeks 48 and 96 using descriptive statistics for each treatment group. Data from other unscheduled assessments will not be included in this summary or analysis. The change from baseline to Weeks 48 and 96 in EDSS scores will be computed and summarized using descriptive statistics for each treatment group.

For the assessment of differences in the mean change in EDSS score during the 96-week comparative treatment period from baseline up to Week 96, MMRM analyses will be undertaken using the same approach as described above in Section 4.4.2.9, except baseline covariates here will be as follows: geographical region (United States vs. ROW) and baseline EDSS (continuous without rounding).

Graphical presentations for least square means and 95% confidence intervals will be used to illustrate trends over time.

4.4.3.21.1 OLE Phase

This analysis will be extended to include data collected during the OLE period. Change from baseline at all scheduled visits until the last mature visit during the combined DB+OLE period and change from OLE baseline at all scheduled visits until the last mature visit during the OLE period will be analyzed.

4.4.3.22 Change in Quality of Life, as Measured by the Short Form 36 Version 2 Mental Component Summary Score from Baseline to Week 96

The derivation of the SF-36 MCS Score was described previously in Section 4.4.2.11.

The MCS Score will be summarized and analyzed in exactly the same way as the SF-36 PCS Score, as described in Section 4.4.2.11.

4.4.3.22.1 OLE Phase

Additional data from the OLE period will be descriptively analyzed.

4.4.3.23 Ratio in Total T2 Lesion Volume as Detected by Brain MRI Scans relative to Baseline at Week 96

The total volume of T2 lesions on MRI scans of the brain will be summarized at baseline and Weeks 24, 48, and 96 using descriptive statistics for each treatment group. Data from other unscheduled assessments will not be included in this summary or analysis. The percentage change from baseline to Weeks 24, 48, and 96 in total volume of T2 lesions on MRI scans of the brain will be computed and summarized using descriptive statistics (e.g., mean, SD, median, minimum, maximum, and n) for each treatment group.

For the assessment of ratio in total T2 lesion volume relative to baseline up to Week 96, MMRM analyses will be undertaken using the same approach as described above in Section 4.4.3.9, except the baseline covariates here will be as follows: log-transformed baseline T2 lesion volume, geographical region (U.S. vs. ROW), and baseline EDSS score (<4.0 vs. ≥4.0).

All T2 lesion volumes below the lower limit of quantification of 0.009 cm³ (3 ,voxels) will be set to this limit.

4.4.3.23.1 OLE Phase

This analysis will be extended to include data collected during the OLE period. Ratio relative to baseline at all scheduled visits until the last mature visit during the combined DB+OLE period and ratio relative to OLE baseline at all scheduled visits until the last mature visit during the OLE period will be analyzed.

4.4.3.24 Ratio in Total T1 Lesion Volume as Detected by Brain MRI Scans relative to Baseline at Week 96

The total volume of T1 lesions on MRI scans of the brain will be summarized at baseline and Weeks 24, 48, and 96 using descriptive statistics for each treatment group. Data from other unscheduled assessments will not be included in this summary or analysis. The percentage change from baseline to Weeks 24, 48, and 96 in total volume of T1 lesions on MRI scans of the brain will be computed and summarized using descriptive statistics (e.g., mean, SD, median, minimum, maximum, and n) for each treatment group.

For the assessment of ratio in total T1 lesion volume relative to baseline up to Week 96, MMRM analyses will be undertaken using the same approach as described above in Section 4.4.3.9, except the baseline covariates here will be as follows: log-transformed baseline T1 lesion volume, geographical region (U.S. vs. ROW), and baseline EDSS score (<4.0 vs. ≥4.0).

All T1 lesion volumes below the lower limit of quantification of 0.009 cm³ (3 ,voxels) will be set to this limit.

4.4.3.24.1 OLE Phase

This analysis will be extended to include data collected during the OLE period. Ratio relative to baseline at all scheduled visits until the last mature visit during the combined DB+OLE period and ratio relative to OLE baseline at all scheduled visits until the last mature visit during the OLE period will be analyzed.

4.4.3.25 Time to Onset of Composite Confirmed Disability Progression (cCDP) for at Least 12 Weeks and at Least 24 Weeks

Time to onset of cCDP over the double-blind treatment period, defined as an increase in EDSS that is sustained for at least 12/24 weeks (0.5 or 1, same criteria as for the secondary endpoint time to onset of 12/24-weeks CDP) or a 20 percent increase in T25-FW that is sustained for at least 12/24 weeks or a 20 percent increase in 9-HPT that is sustained for at least 12/24 weeks. These analyses will be performed for the double-blind period only.

4.4.3.26 Change in EuroQoL 5 Dimension 3 Levels (EQ-5D-3L) VAS and Index from Baseline to Week 48 and Week 96

The EQ-5D questionnaire comprises the following 5 dimensions, each describing a different aspect of health: mobility, self-care, usual activities, pain/discomfort and anxiety/depression. Each dimension has three levels: no problems (1), some problems

(2) and extreme problems (3). This part, called the EQ-5D descriptive system, provides a 5-dimensional description of health status.

A unique health state is defined by combining one level from each of the 5 dimensions. A total of 243 possible health states is defined in this way. Each state is referred to in terms of a 5-digit code. For example, state 11111 indicates no problems on any of the 5 dimensions, while state 11223 indicates no problems with mobility and self-care, some problems with performing usual activities, moderate pain or discomfort and extreme anxiety or depression. The EQ-5D-3L health state is then converted into a single summary number, the EQ-5D-3L index value, using validated translations provided by EuroQoL that can be found in the EuroQoL website (<https://euroqol.org/eq-5d-instruments/eq-5d-3l-about/valuation/>). The EQ-5D-3L index is frequently used in economic evaluations: it represents societal preference values for the full set of EQ-5D-3L health states with the best state (perfect health) and death being assigned values of 1 and 0, respectively.

The United Kingdom value set of this questionnaire will be used for all participants regardless of their country.

The EQ-5D-3L descriptive system is followed by a VAS (EQ VAS), which records the respondent's self-rated health ranging from 0 (worst imaginable health state) to 100 (best imaginable health state).

The EQ-5D-3L index score and VAS score will be summarized at baseline and Weeks 48 and 96 using descriptive statistics for each treatment group. The change from baseline to Weeks 48 and 96 will be also presented.

4.4.3.26.1 OLE Phase

This analysis will be extended to include data collected during the OLE period. Change from baseline at all scheduled visits until the last mature visit during the combined DB+OLE period will be analyzed.

4.4.3.27 NfL

NfL data collected during the double-blind and open label phase will be summarized descriptively. Summary statistics of the absolute NfL values will be presented at all scheduled visits along with the percentage change from baseline. A corresponding plot will be produced. The analyses will be performed for the DB period only as well as for the combined DB+OLE period.

4.4.4 Subgroup Analyses

The primary and some secondary efficacy endpoints (12 and 24 week CDP) will be summarized and analyzed by the following subgroups:

- Demography: age (≥ 40 vs. < 40 years)
- Demography: sex (male vs. female)

- Demography: race (White vs. Other)
- Body weight: ≥ 75 kg versus < 75 kg
- Stratification factor: geographical region (United States vs. ROW)
- Stratification factor: baseline EDSS score (< 4.0 vs. ≥ 4.0)
- Previous lesions: baseline Gd-enhancing lesion (0 vs. > 0)

Estimates of treatment effect and associated 95% CIs will be presented in forest plots. Unadjusted p-values will also be presented for these analyses.

4.4.4.1 Efficacy Data from the Safety Follow-Up Phase

Exploratory analyses of efficacy data collected in the safety follow-up phase are not envisioned.

4.5 PHARMACOKINETIC AND PHARMACODYNAMIC ANALYSES

4.5.1 Pharmacokinetic Analyses

Ocrelizumab serum concentration–time data will be analyzed using a population approach. The primary population PK parameters (clearances and volumes) for ocrelizumab will be estimated by means of a non-linear mixed effect model fitted to the PK data collected in studies WA21092, WA21093, and WA21493. Clearances with associated inter-patient variability may be characterized by a saturable and non-saturable clearance as well as an intercompartmental clearance depending on the final structural model. Volumes with associated inter-patient variability may be characterized by central and peripheral volumes depending on the final structural model. Exposure (area under the concentration–time curve [AUC]) to ocrelizumab will be estimated. The selection of other parameters will depend on the final PK model used for this analysis.

Patients who have measurable concentrations of ocrelizumab will be included in the PK analysis unless major protocol deviations or unavailability of information (e.g., exact blood sampling time) occurred that may interfere with PK evaluation. The influence of covariates, such as age, gender, weight, ADA, and baseline CD19+ cell count on these individual PK parameter estimates will be investigated.

Details will be described in a Modeling and Simulation Analysis Plan, and results will be reported separately from the main CSR.

4.5.2 Pharmacodynamic Analyses

The correlation between individual ocrelizumab exposure and selected safety and efficacy parameters will be explored in order to characterize the exposure and /or dose-response relationship. This may include but is not limited to CD19+ cell count, ARR, infusion-related reactions (IRRs), serious infections, and other safety or efficacy parameters if of interest. Any such analyses will be reported separately in the PK report.

4.6 SAFETY ANALYSES

Safety data include but are not restricted to adverse event data, laboratory data, previous and concomitant treatment data, infusion information including IRR data, withdrawal data, fatalities, ECG, vital signs, ADA data, and dosing information.

This SAP describes the analyses of all available safety data collected until the end of the trial. The safety data will be summarized descriptively for the DBP, OLE and SFU periods:

4.6.1 Exposure of Study Medication

This section deals with exposure in the context of safety analyses. In the context of efficacy analyses, exposure time is as defined above in Section 4.4.

Exposure of ocrelizumab/ocrelizumab placebo and interferon beta-1a 44 µg SC / interferon beta-1a 44 µg SC placebo over the course of the study will be summarized using descriptive statistics.

“Duration of Observation” and “Duration of Exposure” are used interchangeably within this SAP.

Definition of the Dose: A Dose of ocrelizumab can be given as one infusion or two infusions administered 2 weeks apart.

Patients will be considered to have received a Dose of treatment if at least part of one infusion of that Dose (either Day 1 or Day 15 for dual infusions) was given. If a Dose is completely missed instead of delayed, the next Dose number will be based on the number of previous doses received.

The duration of observation for a patient will be calculated as:

$$(\text{Date of last contact}^* - \text{date of first Dose}) + 1$$

* Earliest of 1) date of CCOD for the reporting event, 2) date of last contact from the study completion page, or 3) date of death.

For the controlled treatment period, the CCOD will be variable for each patient at 96 weeks from treatment.

For patients who are receiving interferon beta-1a 44 µg SC and who switch to active ocrelizumab treatment, exposure of interferon beta-1a 44 µg SC will end on the study day prior to their first active Dose of ocrelizumab.

The duration of observation, within a Dose is defined in a similar manner as:

$$(\text{Day prior to first infusion in } n + 1^{\text{th}} \text{ Dose}^* - \text{date of first infusion in } n^{\text{th}} \text{ Dose}) + 1$$

*With the exception of the last Dose received by the patient where date of last contact is used as defined above.

Exposure to ocrelizumab and exposure to interferon beta-1a 44 µg SC during the controlled treatment phase will be summarized. For ocrelizumab, the treatment duration, number of infusions received, and the total cumulative dose (derived to mg) will be summarized by study treatment arm. An additional summary will be presented, summarizing at each infusion the percentage of patients who received <80% and ≥80% of the planned infusion. The number and percentage of infused patients who were pre-treated with steroids will be summarized. For interferon beta-1a 44 µg SC, the number of Doses and dose intensity (based on the number of syringes received rather than the actual Dose) will be presented by study treatment arm.

4.6.2 Columbia-Suicide Severity Rating Scale

The number and percentage of patients with suicidal ideation, suicidal behavior, and self-injurious behavior without suicidal intent at any time after the start of study treatment, based on the Columbia Suicide Severity Rating Scale (C-SSRS), will be presented. In addition, shift tables will be presented to show changes from baseline in C-SSRS categories. A listing of patients with suicidal ideation, suicidal behavior, or self-injurious behavior, based on the C-SSRS, will be presented.

4.6.3 Adverse Events

Adverse events will be defined as all adverse events including IRRs and serious MS relapses, but excluding non-serious MS relapses. Therefore, those adverse events recorded on the “adverse event” and “infusion-related reaction” CRF pages will be included.

For each adverse event recorded, the term entered by the investigator describing the event (the “reported term”) will be assigned a standardized term (the “preferred term” [PT]) based on the Medical Dictionary for Regulatory Activities (MedDRA) World Health Organization (WHO) dictionary of terms. All analyses of adverse event data will be performed using the PTs unless otherwise specified.

All adverse events will be mapped to PTs and super class terms. For all summary tables, the adverse events will be sorted by body system (in decreasing order of overall incidence) and then by PT (in decreasing order of overall incidence). Additionally, the most frequent adverse events (≥5% in any treatment arm) will be presented by PT.

Adverse events will be assigned to a Dose if the adverse event onset date is on or after the date of the first infusion of that Dose, but before the first infusion of the next treatment Dose. Adverse events that are reported during the safety follow-up period or B-cell monitoring period will be assigned to the last Dose received. Hence the last Dose for a patient may be of a variable length from 24 to 72 weeks or longer. Adverse events

that start prior to the first Dose and worsen during treatment (i.e. treatment emergent) will be assigned to the first treatment Dose.

All summaries and listings of adverse events will be based on the safety population unless otherwise stated. Summaries of adverse events will be generated by summarizing the incidence of treatment-emergent adverse events only. Treatment-emergent events are defined as those adverse events with observed or imputed onset date on or after the start date of study treatment. Only where the most extreme intensity is greater than the initial intensity will events with an onset date prior to the start of study treatment (and with an end date on or after the start of study treatment) be considered treatment emergent. An adverse event with a completely missing non-imputed start date will be assumed to be treatment emergent unless the adverse event has a complete non-imputed end date that is prior to start of study treatment.

For each treatment group, the incidence count for each adverse event PT will be defined as the number of patients reporting at least one treatment emergent occurrence of the event. The incidence rate will be calculated as the incidence count divided by the total number of patients in the population. Each table will also present the overall number of patients experiencing at least one adverse event and the total number of adverse events reported (multiple occurrences of the same adverse event in 1 patient will be counted only once).

The number of patients who experienced a related adverse event will be summarized by system organ class (SOC) and PT. Adverse events will be summarized by SOC and PT by intensity grade. Multiple occurrences of the same event within a patient will be counted once at the greatest intensity/highest grade for this PT. For adverse events leading to death, the most extreme intensity will be overwritten by Grade 5 (death). Any adverse events and the SOC overall rows of the summary table will count patients according to adverse events by intensity/grades.

All patient deaths, regardless of treatment received, will be listed.

Serious adverse events will be defined as all serious adverse events including serious MS relapses and serious IRRs. The number of patients who experienced a serious adverse event will be summarized by SOC and PT. Related serious adverse events will be summarized by SOC and PT. Additionally, the most frequent serious adverse events ($\geq 1\%$) will be presented by PT.

A separate listing with relapses considered as serious adverse events will be presented.

A patient may experience an adverse event that leads to the discontinuation of their study treatment. Discontinuation of study treatment for an adverse event may not necessarily lead to discontinuation from the study because patients can enter the safety follow-up periods of the protocol. Only adverse events that led to the discontinuation of

study treatment are of interest. Patients who withdraw early from the study because of adverse events will be summarized under disposition. Because of the double-dummy design, the study-drug regimen consists of more than one combination of two treatments (ocrelizumab and interferon beta-1a 44 µg SC). An analysis of adverse events leading to study drug discontinuation will not be performed for the individual treatments of the regimen within one study arm, because the investigators were instructed to discontinue both treatments. The number of patients who experienced an adverse event that led to discontinuation of study treatment will be summarized by SOC and PT.

The number of patients who experienced an adverse event that led to modification or interruption of study drug will be summarized by SOC and PT.

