4.6.3.1 Selected Adverse Events

Infection

Infections will be defined from the adverse event data using the MedDRA SOC of “Infections and Infestations.” During Primary CSR, adverse events that are reported as an infection by the investigator will also be included.

During Primary CSR, an infection has been defined as serious if the event is a serious adverse event or if the non-serious infection was treated with an IV anti-infective. For subsequent reporting, an infection has been defined as serious if the event is a serious adverse event.

The number of infections and serious infections per 100 patient-years will be calculated and summarized separately. The ninety-five percent CI of the incidence rates will be calculated using exact method based on Poisson distribution.

Summary of infections will be presented by SOC and PT, severity, and Dose. Similar summary tables will be also produced by serious infections.

Summary tables of infections and serious infections by pathogen information codes as well as listing of infections/serious infections with pathogen codes will be produced.

Infusion-Related Reactions

An IRR and its corresponding symptoms are collected on the dedicated eCRF.

The symptom(s) of an IRR and the IRR itself may be of different intensities. As other symptoms can be recorded as free-text on the eCRF page, symptoms will be coded in the MedDRA and summarized by PTs.

IRRs are categorized by the time of the event occurring (1) during the infusion, (2) after completion of the infusion while patient is in the clinic, and (3) within 24 hours of completion of the infusion and patient is not in the clinic. The number and percentage of patients with at least one IRR will be presented by infusion (patients with multiple events within an infusion will count only once). In addition, the total number of IRRs will be

summarized (multiple events will be counted). The total and percentage (based on the total number of patients with at least one IRR) will be summarized by most extreme intensity.

IRRs will be summarized by intensity and by infusion. For multiple events within a patient, the most extreme intensity will be taken.

Symptoms of IRR and symptoms of serious IRR will also be presented by infusion. This analysis will be produced for both the controlled treatment period and the OLE period.

The number of patients with at least one IRR, the total number of IRRs, and the number of IRRs will be summarized by the time of events.

Pregnancies

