4.6.7 Safety by Treatment and Period

To explore safety by treatment and period, all of the available safety data will be presented by treatment regimen and by period (i.e., All periods and OLE period separately, as appropriate).

The adverse event profile will be produced by treatment regimen for each period separately. The number of events per 100 patient-years will be presented to account for differing amounts of exposure.

Adverse events and serious adverse events will be presented by SOC and PTs for each period separately. Also, infection and serious infection will be presented by SOC and PTs for overall as well as each period separately.

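### SAP 4.6.3 labels a once-per-patient-per-term count as the total number of adverse events, and the numerator of the rates per 100 patient-years is not stated

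*SAP*

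**What the plan says.** SAP 4.6.3 sets out a patient-level measure first. The incidence count for a preferred term is "defined as the number of patients reporting at least one treatment emergent occurrence of the event", and "The incidence rate will be calculated as the incidence count divided by the total number of patients in the population". Each table must also give the number of patients with any adverse event and "the total number of adverse events reported (multiple occurrences of the same adverse event in 1 patient will be counted only once").

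SAP 4.6.3.1 uses the opposite convention for infusion-related reactions: their total is to be "summarized (multiple events will be counted"). The opening of 4.6.3 classes these reactions as adverse events.

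Person-time rates appear in two places. In 4.6.7: "The number of events per 100 patient-years will be presented to account for differing amounts of exposure". In 4.6.3.1: "The number of infections and serious infections per 100 patient-years will be calculated and summarized separately", with an exact Poisson confidence interval. Neither place says whether repeat occurrences in a patient enter the numerator.

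**The concern.** Once-per-patient counting is right for an incidence count. Applied to a figure presented as the total number of events, it removes the recurrence information that a total should carry. A reader of the report would take patient-term pairs for events. The same infusion-related reactions would also yield two different totals in one report.

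The unstated numerator is a separate gap. A programmer looking for a general counting rule for adverse events finds the capped one in 4.6.3. In addition, 4.6.3.1 calls its person-time figures incidence rates, a term that 4.6.3 ties to once-per-patient counting. Protocol 4.1.6.7 gives long-term safety, including infections and serious infections, as a purpose of the extension. A numerator that saturates while person-time grows would blur that question.

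**Working it through.** The documents give no figure that depends on this rule, so there is nothing of the plan's own to reproduce. The check models one preferred term under the two counting rules.

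**Inputs**
- Controlled period: 96 weeks, T = 96 × 7 / 365.25 = 1.84 years ("For the controlled treatment period, the CCOD will be variable for each patient at 96 weeks from treatment", SAP 4.6.1).
- Extension: SAP 2.4 dates the primary cutoff for this study at 12 May 2015, about 12 weeks after the last Week 96 visit, so that visit falls around 17 February 2015. From there to 31 December 2022 is about 7.9 years for a continuing patient. Total follow-up is then 1.84 + 7.87 = 9.71 years. A rounder T = 7 years is assumed for the extension alone.
- Rate λ per patient-year for one term: assumed, because the documents give none for this trial.
- Recurrence: assumed homogeneous Poisson.

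**Formulas**
- All occurrences per 100 patients: 100 λT.
- Capped count per 100 patients: 100 (1 − exp(−λT)).
- Rate per 100 patient-years from the capped count: 100 (1 − exp(−λT)) / T.

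**Step 1: the reported total** (per 100 patients, all occurrences vs capped)

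| λ | 96 weeks | Undercount | 9.7 years | Undercount |
|---|---|---|---|---|
| 0.10 | 18.4 vs 16.8 | 9% | 97.1 vs 62.1 | 36% |
| 0.25 | 46.0 vs 36.9 | 20% | 242.7 vs 91.2 | 62% |
| 0.50 | 92.0 vs 60.1 | 35% | 485.4 vs 99.2 | 80% |

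The capped total always rises, and the share of events it misses grows.

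**Step 2: arms compared at equal 96-week follow-up.** A true two-fold difference in capped totals shrinks to 1.83 (λ 0.10 vs 0.20), 1.63 (0.25 vs 0.50) or 1.40 (0.50 vs 1.00).

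**Step 3: a person-time rate, if the capped count were its numerator.** For λ = 0.20: 100 (1 − exp(−0.368)) / 1.84 = 16.7, and 100 (1 − exp(−1.4)) / 7 = 10.8.

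| True rate per 100 PY | Over 96 weeks | Over 7 years | Apparent fall (unrounded rates) |
|---|---|---|---|
| 5 | 4.8 | 4.2 | 12% |
| 10 | 9.1 | 7.2 | 21% |
| 20 | 16.7 | 10.8 | 36% |
| 30 | 23.1 | 12.5 | 46% |

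With all occurrences counted, each row would show its true rate in both columns.

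**Step 4: sensitivity.** With gamma frailty of variance 1 and λ = 0.25, the capped rate goes from 17.1 at 96 weeks to 7.3 at 9.7 years, against 20.0 to 9.4 without frailty. The direction is unchanged. As a case anchored in the documents, Protocol 2.1.4.1 gives a Phase II low-dose serious-infection rate of 3.39 per 100 patient-years. Treated as one term, it would read 3.29 over 96 weeks and 3.02 over 7 years, a fall of about 8%.

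**The case against.** The capped rule is attached to incidence tables whose denominator is patients, and nothing in 4.6.7 or 4.6.3.1 invokes it for person-time rates. Wording in terms of numbers of events or infections, with a Poisson interval, fits counting every occurrence. The SAP contains both conventions, since infusion-related reactions are counted in full. Infections are also summarised by Dose, and events are assigned to Doses by onset date, so a recurrence in a later Dose would still appear there. Periods are shown separately ("Adverse events and serious adverse events will be presented by SOC and PTs for each period separately"). Pooled long-term safety follows a separate pooling SAP that is not available here. Finally, a single term at 20 per 100 patient-years is a high assumption: the Phase II low-dose rate for all infections together was 92.41.

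Most of this stands, and it rules out two stronger readings. A reader might infer that event totals fall as follow-up lengthens; they cannot, because a capped count only rises and levels off. A reader might also infer that the plan's long-term rates are biased towards reassurance. The text does not support that, because the numerator is unspecified rather than shown to be capped.

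None of it makes the total in 4.6.3 correct. There the cap is written out as the rule. Dose-level and period-level tables limit its reach without changing what the figure counts.

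**Conclusion.** The point holds in two parts. First, without any modelling assumption: the total required by 4.6.3 is a count of patient-term pairs under the wrong label, and it is inconsistent with the infusion-reaction total in 4.6.3.1. Its undercount depends on how recurrent the term is: 9% to 35% at 96 weeks and 36% to 80% at 9.7 years for assumed rates of 0.10 to 0.50 per patient-year.

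Second, conditionally: if the same count fed the rates per 100 patient-years, a constant rate would seem to decline between the 96-week period and the extension. The decline would be a little over a third for a term at 20 per 100 patient-years, and about 12% or less at 5 or fewer. These sizes rest on assumed per-term rates, Poisson recurrence and an assumed 7-year extension. The length effect concerns mainly extension and all-period tables, since controlled-period exposure is cut at 96 weeks in both arms.

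This affects descriptive safety reporting only. It is worth correcting before the final report because the change is small and the figure is one that readers will use.

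**What to change.** In SAP 4.6.3, count every treatment-emergent occurrence in the total number of adverse events, and keep once-per-patient counting for the incidence count and incidence proportion only. In 4.6.7, and for infections in 4.6.3.1, state that the numerator is all occurrences in the period and the denominator is all person-time in that period, and show patient-level incidence beside the rate.

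The cost is a few lines of wording and a programming setting. If the rate programs already count every occurrence, the change to those sections only documents it. The downside is comparability. Final-report totals will be larger, and SAP 2.4 lists the primary report and the yearly cuts up to 2021 as completed. Any of those tables that used the capped total need a footnote or a rerun before they are set beside the final ones.
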